- Adverse events (recorded at supervised exercise sessions or reported from home sessions)
- Time commitment per participant (for participants, calculated as sum of hours exercising; for staff, calculated as [hours spent supervising exercise / number of individuals supervised simultaneously + hours spent scheduling and/or coordinating for that participant])
- Qualitative feasibility collected via narrative survey of participants and staff

B. Description of Population to be Enrolled:

Men and women ages 18-65 with deployment-related respiratory disease and symptoms of exertional dyspnea or exercise intolerance residing in the Veterans Integrated Service Network (VISN) 19 and receiving some or all of their care at VA medical facilities throughout the Eastern Colorado Health Care System (ECHCS) will be recruited. We will enroll up to 12 eligible veterans.

- **Inclusion Criteria:**

- Deployment of ≥ 30 days to Iraq, Afghanistan, Kuwait, Saudi Arabia, Bahrain, Qatar, United Arab Emirates, Kyrgyzstan, or Djibouti after September 2001(11)
- New onset of cough, shortness of breath, chest tightness/wheezing, dyspnea on exertion or exercise intolerance which started during or after deployment(11)
- Definite or probable distal lung disease (≥ 1 hyperinflation, emphysema, bronchiolitis, small airways inflammation, peribronchiolar fibrosis, or granulomatous pneumonitis on surgical lung biopsy; or ≥ 2 centrilobular nodularity, air trapping, mosaicism, or bronchial wall thickening on chest CT),(11) definite or probable deployment-related asthma (≥ 1 increase in post-bronchodilator forced expiratory volume in 1 second [FEV₁] $\geq 12\%$ and ≥ 200 cc, or methacholine challenge with PC₂₀ FEV₁ ≤ 16 mg/mL)(11) or unexplained dyspnea on exertion or exercise intolerance despite noninvasive testing including pulmonary function testing, methacholine challenge, transthoracic echocardiography, and/or chest computed tomography(9, 13)
- Current symptoms of dyspnea on exertion or exercise intolerance
- Residence <90 miles from RMR VA and ability / willingness to attend in-person HIIT sessions and research visits

- **Exclusion criteria:**

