- Active / uncontrolled cardiovascular or pulmonary disease (e.g. hypertension with blood pressure $>160/100$ despite antihypertensive therapy, known hypertensive response to exercise [systolic blood pressure >220 mmHg in men / >190 mmHg in women], coronary artery disease, left ventricular ejection fraction $\leq 45\%$ or heart failure with preserved ejection fraction with ongoing symptoms despite diuretic therapy, uncontrolled arrhythmia, moderate or severe valvular abnormality, diabetes with HbA_{1c} $>8.5\%$ documented within the prior year, chronic obstructive

[figure not shown]
- pulmonary disease or asthma exacerbation requiring steroids within 4 weeks of enrollment, , interstitial lung disease, untreated severe obstructive sleep apnea)
- Pre-deployment history of cardiovascular or pulmonary disease including coronary artery disease, left ventricular ejection fraction $\leq 45\%$ or heart failure with preserved ejection fraction requiring diuretic therapy, arrhythmia, valvular abnormality, chronic obstructive pulmonary disease, asthma (excluding childhood asthma that did not persist into adulthood), interstitial lung disease, or pulmonary hypertension
- Body mass index <18.5 or $>45 \text{ kg/m}^2$
- Anemia with hemoglobin $<10 \text{ g/dl}$
- Disorders that adversely influence exercise ability or ability to complete CPET and HIIT intervention using an upright stationary bicycle (e.g. arthritis or peripheral vascular disease)
- Current fitness program (e.g. >30 minutes at METs >6 3 times/week or more or >90 minutes spent at METs $>6/\text{week}$)(8)
- Pregnancy or possible anticipated pregnancy during study duration
- Breastfeeding status
- Respiratory symptoms determined to be due to alternative cause, including long COVID

Potential participants evaluated at the recruitment sites typically undergo significant evaluation for respiratory symptoms to exclude causes unrelated to deployment-related respiratory disease, increasing the feasibility of applying the exclusion criteria. Additionally, participants may be excluded at the discretion of Principal Investigators (PIs Drs. [name], [name] and [name]) if any conditions are discovered during screening that may increase risk of study participation.

C. Study Design and Research Methods

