Anticipated risks of HIIT training include fatigue, shortness of breath and leg discomfort, and participants will be counseled of these risks. Additionally, study team will closely monitor for adverse events through observation as well as participant report. Adverse events will include the following: minor – hypotension (BP < 90/60), lightheadedness, hypoxemia (SpO₂ <80% for >60 seconds),(24) chest pain, arrhythmia, or need to terminate exercise for another reason; major – major adverse cardiac event (stroke, myocardial infarction or cardiovascular death) or hospitalization. Exercise session will be terminated for any minor adverse event and PI and study safety monitor will be notified. Patient will be referred to Emergency Room if any member of the study team or the participant feel referral is indicated. Additionally, participant will be evaluated by PI prior to engaging in any future sessions. If further participation is felt to be of risk to the patient by either PI or the study’s safety monitor, then participation in study will be terminated. Major adverse events are not anticipated, but if any should occur patient will be transported immediately to the Emergency Room. HIIT has been studied in various populations including those with good health but sedentary lifestyle,(8) moderate to severe asthma,(17) and coronary artery disease,(25) and similar or identical HIIT regimens to that described in this protocol studies have demonstrated >80% compliance without attributable adverse events.(8, 25) Additionally, the study design includes an initial baseline assessment with symptom-limited CPET. If the initial CPET identifies safety concerns with completing the study exercise protocol, those concerns will be addressed prior to participant completing any further intervention. If unable to be addressed then the participant will be removed from the study. Therefore, the proposed protocol is anticipated to be safe for participants.

Home exercise: In addition to HIIT sessions described above, participants will perform three sessions / week of 40 minutes aerobic exercise at moderate intensity (Borg rate of perceived exertion 12-14). Home exercise will be prescribed to minimize the risk of confounding from

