Feasibility of exercise training program: A three-week familiarization / physiologic adaptation period has been built into the HIIT program to maximize the likelihood of participants being able to successfully perform the exercise training program. However, there is still the possibility of individuals being unable to complete the full intended training program due to injury or other reasons. Successful completion of HIIT sessions (including meeting target heart rate) will be assessed by the study team at least every 4 weeks. If an individual demonstrates >3 sessions over a 4-week period in which they fail to meet the exercise prescription, a study team member will discuss with the participant barriers to meeting the exercise prescription and help identify ways to address those barriers as appropriate. If an individual develops an injury which prevents them from completing the prescribed exercise program, they will be transitioned to a continuous exercise training regimen if possible (i.e. substituting "light exercise" training sessions for HIIT sessions) until able to resume HIIT, at which time they will begin HIIT with a repeat three-week familiarization / physiologic adaptation period. If they are unable to complete continuous exercise training, they will discontinue exercise training until able to resume. Completion rates of HIIT and continuous exercise training will be assessed as part of the analysis of the study (Aim 2).

E. Data Analysis Plan:

Specific Aim 1:

Hypothesis 1A: Pulmonary vascular remodeling resulting from prior airborne hazards exposures increases exertional pulmonary arterial pressure and right ventricular afterload, resulting in compromised right ventricular exertional performance with abnormal oxygen pulse, ventilatory inefficiency and increased dead space fraction on CPET and increased pulmonary artery systolic pressure during exertion (relative to healthy population norms).(4) Oxygen pulse, ventilatory efficiency, and dead space fraction will be analyzed using descriptive statistics. Results will be presented in reference to healthy population norms (ATS/ACCP guidelines).(6) Pulmonary artery systolic pressure will be analyzed using descriptive statistics. Results will be presented in reference to healthy population norms (American Society of Echocardiography guidelines).(5)

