Hypothesis 1B: Increased right ventricular afterload causes maladaptive right ventricular remodeling which is reflected by increased glycolytic metabolites (compared to a reference healthy population).(2, 3) Metabolomics partial least squares discriminant analysis and t-test or ANOVA will be performed. Exercise metabolomics data collected in a healthy population (COMIRB 21-4354) will be used as a reference.

Hypothesis 1C: Impaired right ventricular performance contributes to reduced maximum oxygen consumption (VO2max) relative to healthy population norms, dyspnea and impaired health-related quality of life. VO2max will be analyzed using descriptive statistics and presented in reference to healthy population norms (ATS/ACCP guidelines).(6) Dyspnea and health-related quality of life will be assessed by SF-36 with scores analyzed by descriptive statistics. Scores will be presented in

reference to disease population references.(34, 35) Linear mixed models will be used to assess the relationship between impaired right ventricular performance as measured by pulmonary artery systolic pressure and VO2max. Covariates including BMI, gender, age and type of deployment-related respiratory disease will be included.

Specific Aim 2:

Hypothesis 2A: *HIIT is safe and feasible among military personnel suffering from deployment-related respiratory disease, with $\geq 80\%$ participation in prescribed sessions.*(8) Attendance will be calculated as (number of supervised sessions attended + unsupervised sessions reported by exercise diary) / total number of supervised + unsupervised sessions. Feasibility will be based upon attendance of $>80\%$ of prescribed exercise sessions, with separate analyses for HIIT sessions, “light exercise” sessions, and combined sessions. Safety/acceptability will be based upon an absence of major adverse events attributable to the exercise training program and $<5\%$ minor adverse events (calculated as the number of adverse events divided by the total number of exercise sessions throughout the program) attributable to the exercise training program.

Hypothesis 2B: *Participants will spend approximately 4.5 hours/week engaged in this program and will report that participation was feasible.* Total hours spent in exercise program will be calculated based upon number of supervised sessions and reported unsupervised sessions. Qualitative assessment of feasibility will be collected via narrative report.

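### The Hypothesis 2A safety rule has no clear class for some exacerbations and injuries, and its per-session rate passes even with all 12 participants affected

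*Combined protocol and SAP*

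**What the plan says.** The event definitions are in section III.D, under HIIT intervention. Minor events are hypotension, lightheadedness, hypoxemia, "chest pain, arrhythmia, or need to terminate exercise for another reason". The other class is "major – major adverse cardiac event (stroke, myocardial infarction or cardiovascular death) or hospitalization". The next sentence ties minor events to a session: "Exercise session will be terminated for any minor adverse event and PI and study safety monitor will be notified".

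The criterion is in the Data Analysis Plan, Hypothesis 2A: "Safety/acceptability will be based upon an absence of major adverse events attributable to the exercise training program", together with attributable minor events below 5%, "calculated as the number of adverse events divided by the total number of exercise sessions throughout the program".

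Three other places bear on the point.

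- **Population (III.B).** "We will enroll up to 12 eligible veterans", who may have asthma, distal lung disease or unexplained dyspnea. Exacerbation appears only among the exclusions, as "pulmonary disease or asthma exacerbation requiring steroids within 4 weeks of enrollment".
- **Injury (Potential Scientific Problems, on feasibility of the training program).** "If an individual develops an injury which prevents them from completing the prescribed exercise program", the participant moves to continuous exercise or pauses. Completion rates are then analysed under Aim 2.
- **Collection (III.C and III.D).** The home diary has a field for symptoms and adverse events, participants are questioned every 4 weeks, and adverse events go to the safety monitor at once.

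**The concern.** The protocol itself foresees both kinds of harm: exacerbation as a reason not to enrol, and injury as a reason to suspend HIIT. Neither is named in the definitions that decide whether HIIT is called safe. An exacerbation that starts some hours after training and is treated at home, or an overuse injury that develops between sessions and keeps someone off HIIT, may therefore leave the safety result untouched.

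The denominator adds to the problem. Each participant contributes dozens of sessions, so a percentage of sessions can look small when every person has been affected. Safety is part of Aim 2 and of the stated primary objectives, and the results are meant to justify a randomized trial. A safety statement that does not respond to these events would pass to that trial with more confidence than the data support.

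**Working it through.** **Step 1. Where attributable events fall under the written definitions**

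| Event | Class in III.D | Effect on the safety criterion |
|---|---|---|
| Exacerbation or injury leading to admission | Major (hospitalization has no stated cause) | A single event fails it |
| Exacerbation or injury that ends a session, no admission | Minor, through the catch-all | Adds one to the numerator |
| Exacerbation treated without admission that ends no session | No clear class | None, or one minor event if read in |
| Injury that suspends HIIT without ending a session | No clear class; handled through completion rates | None, or one minor event if read in |

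The gap is confined to the last two rows.

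**Step 2. Session counts.** The plan gives no session total, so it is built from stated inputs: 12 participants, 12 weeks, 3 supervised and 3 home sessions a week. As a check on duration, the compensation section allows 27 + 27 = 54 hours of exercise, and 54/12 = 4.5 hours a week. This is the figure in Hypothesis 2B, so 12 full weeks is the planning basis.

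- HIIT sessions: 12 × 12 × 3 = 432, or 36 per participant.
- Combined sessions: 12 × 12 × 6 = 864, or 72 per participant.
- At 80% attendance: 0.8 × 432 = 345.6 and 0.8 × 864 = 691.2.

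Both denominators are shown because the criterion does not say whether it means HIIT or combined sessions, or prescribed or attended ones.

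**Step 3. One event in each of 12 participants, none admitted.** Major events = 0. Minor-event rate = events / sessions:

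| Handling | HIIT sessions | Combined sessions |
|---|---|---|
| Not counted | 0% | 0% |
| Counted as minor, full attendance | 12/432 = 2.8% | 12/864 = 1.4% |
| Counted as minor, 80% attendance | 12/345.6 = 3.5% | 12/691.2 = 1.7% |

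Every cell is below 5%. In general, one event each passes when 1/s < 0.05, that is, with more than 20 sessions (s) per participant.

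**Step 4. Room in the rule.** 0.05 × 432 = 21.6, so 21 minor events pass on HIIT sessions. 0.05 × 864 = 43.2, so 43 pass on combined sessions. Two events each give 24/432 = 5.6%, which fails, or 24/864 = 2.8%, which passes.

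**Step 5. Participant level.** The scenario in Step 3 is 12/12 = 100% of participants. At the other extreme, 0/12 has an exact two-sided 95% upper limit of 1 − 0.025^(1/12) = 26.5%. The per-session rule shows neither figure.

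**The case against.** The strongest reply is that the protocol covers more than a quick reading suggests, and much of that reply stands.

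- A reader might infer that the definitions are purely cardiac. They are not: hypoxemia, hospitalization for any cause and a general reason to stop exercise are all included.
- A reader might infer that exacerbations and injuries are left out altogether. They are not: those leading to admission are major, and those ending a session are minor.
- A reader might infer that such harms would go unseen. The diary, the 4-weekly questioning and the safety monitor, who also reviews after six participants and at the end, make that unlikely. The difficulty is that seeing an event does not make it count in the criterion.
- Prolonged injury does bear on Hypothesis 2A as a whole. If every participant missed three weeks of HIIT, 9 of 36 sessions would be lost, attendance would be 27/36 = 75%, and the separate HIIT attendance analysis would fail its 80% mark (assuming missed sessions are not replaced and the denominator is unchanged). The safety limb would still pass.
- The catch-all could be read broadly enough to take in a suspension of training. Step 3 shows that this does not change the outcome for one event each.

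It is also fair that this is a 12-person single-arm pilot with acknowledged limits, and that one event in every participant is an extreme case. The documents give no exacerbation or injury rate. The scenario shows what the rule tolerates and predicts nothing.

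**Conclusion.** The concern holds in a limited form. The safety limb of Hypothesis 2A gives no clear class to an attributable exacerbation treated without admission, or to an exercise-related injury that suspends HIIT, when the event does not end a session. One such event in all 12 participants satisfies the criterion, at 0% if uncounted and 1.4% to 3.5% if counted as minor. The per-session denominator drives this at least as much as the event list, because naming the events as minor would not alone change the result.

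A reader might go further and infer that repeated events per person would always pass. The documents do not support that: two counted events each fail on HIIT sessions (5.6%) and pass only on combined sessions (2.8%). Nor do they show that training provokes exacerbations; the steroid criterion is an entry screen.

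The figures assume 12 participants, a full 12 weeks (the protocol says up to) and that all events are judged attributable. The documents define neither attribution nor who decides it. This should be corrected, since it bears on a main conclusion and costs little.

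**What to change.** **In III.D (definitions).** Name two event types as adverse events whatever their onset relative to a session: a respiratory exacerbation, in the protocol's own sense of requiring steroids, and an exercise-related injury that suspends or stops HIIT. The sponsor should state the class of each for Hypothesis 2A. Both should be asked about at the existing 4-weekly contact. The management steps now attached to each class are outside this point.

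**In the Data Analysis Plan, Hypothesis 2A.** Beside the per-session rate, report the number of participants with at least one attributable adverse event, overall and for each of the two types, with an exact 95% confidence interval. State which sessions form the denominator. Then choose one of two routes in advance:

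- base the safety statement on both measures, with a participant-level threshold set by the sponsor; or
- limit the statement to having met the per-session criterion, and give the participant-level estimate next to it.

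**Cost.** Definition wording, two items at an existing contact and one table, with no change to the intervention or sample size. The downside is slightly more event recording and a possibly less favourable safety statement.

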HIIT exercise intervention: HIIT sessions will be administered at the outpatient University of Colorado Clinical and Translational Research Center through the Investigations in Metabolism, Aging, Gender and Exercise (IMAGE) Research Group exercise lab. HIIT intervention will include 3 weekly supervised sessions (10 minutes warm-up followed by 4 x 4-minute intervals [4 minutes at 90-95% peak heart rate followed by 3 minutes at 60-75% peak heart rate]).(7) HIIT sessions will be performed on an upright stationary bicycle. Additionally, participants will be requested to complete 3 40-minute sessions of moderate aerobic exercise each week (Borg rate of perceived exertion 12-14). Aerobic exercise may be performed using any exercise modality. During the first three weeks of the exercise program, the exercise prescription will be modified to facilitate orientation to the training program and physiologic adaptation. Specifically, the first session will be performed with one-on-one supervision from a research coordinator. The coordinator will assist with identifying appropriate an exercise workload based upon the baseline CPET. Subsequent sessions will be performed with ready availability of coordinators to ensure heart rate targets are achieved. The first week of the program HIIT sessions will be modified to include 1 x 4 minute intervals (with a 10-minute warm-up and 3-minute cool-down for a total of ~20 minutes exercise). The second week HIIT sessions will include 2 x 4 minute intervals (with a 10-minute warm-up and 6-minute cool-down for a total of ~30 minutes exercise). The third week HIIT sessions will include 3 x 4 minute intervals (with a 10-minute warm-up and 4-minute cool-down for a total of ~35 minutes exercise). During the first week participants will complete home sessions of 20 minutes aerobic exercise. During the second week participants will complete home sessions of 30 minutes aerobic exercise. During the third week participants will complete home sessions of 35 minutes aerobic exercise. Participation and adverse events will be recorded at supervised sessions and through a diary of home aerobic sessions including time, activity, heart rate at approximately half-way point of exercise, symptoms and adverse events. The exercise diary will be recorded via REDCap MyCap (mobile device application to capture participant reported outcomes) or on paper according to participant preference.

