paradoxical decrease in non-HIIT day physical activity (an effect described in the literature of exercise training interventions).(26) The home exercise program will include a three-week “phase-in” period as described in the protocol above. Participants will keep a diary of home exercise as described above in “Study Design and Research Methods” that includes a field for symptoms and adverse events. Study personnel will collect the diary at 4-week intervals and at that time will also question participant regarding any adverse events not reported through other means. Home exercise has been studied in populations including those with chronic lung disease and pulmonary arterial hypertension without significant attributable adverse effects.(27, 28) Additionally, as described above all participants will undergo baseline CPET and if risks to engaging in an exercise regimen are identified they will be addressed prior to any further intervention.

Risks to a pregnant woman, embryo or fetus: Due to physiologic changes of pregnancy which are anticipated to impact response to exercise training, pregnant women will be excluded from this study. Women of child-bearing age will complete a urine pregnancy test prior to testing during Visit 1. If the test is positive, the participant will be informed and removed from the study. Additionally, participants will be counseled to avoid pregnancy during the study and will be removed from the study should pregnancy occur.

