Loss of confidentiality: Data to be collected include demographics, health conditions, and study information including results of testing and exercise monitoring (including heart rate during HIIT sessions and exercise diaries). Study data will be stored in a deidentified fashion. Only the PI's will have access to the deidentification code. Data collected via internet applications or mobile devices, such as questionnaires (REDCap, MyCap) and heart rate data (Polar Flow application), will be de-identified/anonymized. While every effort will be made to keep participant information confidential, there is a potential risk of loss of confidentiality any time information is collected. Additionally, loss of confidentiality may occur through participants' participation in a gym exercise setting. However, the only personal information which will be used in that setting will be participant name, and heart rate monitoring will be done in a deidentified format. All research personnel involved in the study are trained in protecting privacy and confidentiality. Participants will be counseled regarding the nature of the information stored, the risk of loss of confidentiality, and the measures in place to maintain confidentiality.

Additional safety measures:

- Participants may withdraw from study at any time for any reason. All participants will be counseled regarding this component during informed consent process.
- A study safety monitor with dual University of Colorado and VA appointments will be appointed. The study monitor will review the study after six participants have completed the study protocol and again after all participants have completed the study protocol. Additionally, any adverse events will be reported immediately to safety monitor and any that are determined to be unexpected, related to the research intervention, or serious will be reported to the IRB.

E. Potential Scientific Problems:

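### Adverse events must reach the safety monitor immediately, but for home sessions the only scheduled capture is 4-weekly and no prompt route is specified

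*Combined protocol and SAP*

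**What the plan says.** Four places in the combined protocol and SAP bear on this.

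- **Section III.D, Additional safety measures.** "any adverse events will be reported immediately to safety monitor". No setting is exempted. The same bullet schedules the monitor's own reviews after six participants have completed the protocol and again after all have.
- **Section III.D, HIIT intervention.** The team's general commitment is that "study team will closely monitor for adverse events through observation as well as participant report". On a minor event, "Exercise session will be terminated for any minor adverse event and PI and study safety monitor will be notified", and the "participant will be evaluated by PI prior to engaging in any future sessions". Minor events include chest pain, arrhythmia and lightheadedness.
- **Section III.D, Home exercise.** The diary has space for adverse events and symptoms. Its timetable is this: "Study personnel will collect the diary at 4-week intervals". A second step is tied to that collection, when staff "at that time will also question participant regarding any adverse events not reported through other means".
- **Section III.C, HIIT exercise intervention.** Adverse events are recorded at supervised sessions and, for home exercise, in the diary. "The exercise diary will be recorded via REDCap MyCap (mobile device application to capture participant reported outcomes) or on paper according to participant preference". No frequency is given for reviewing app entries.

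Section III.A counts events reported from home sessions within the adverse-event outcome, so home events are in scope.

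**The concern.** Immediate reporting works only if staff learn of an event soon after it happens. At supervised sessions they do, because they are present. At home, the first place an event is written down is the diary, and the only scheduled point at which staff read it, or ask about anything missing from it, comes every 4 weeks. A participant could record chest pain during a home session and then attend high-intensity sessions that week and in the following weeks without anyone on the study team knowing.

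What is at stake is the ability of the monitor and the PI to act during a participant's training. The monitor's two scheduled reviews are tied to participants completing the protocol. For someone still in the programme, event-by-event reporting is the route by which the monitor would hear of a problem in time to use the role that the HIIT paragraph gives the monitor in deciding on continued participation.

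**Working it through.** The plan states no figure to reproduce. The check is to set the passages side by side and then count.

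**Inputs**
- Supervised sessions: 3 a week (Section III.C).
- Home sessions: 3 a week (Sections III.C and III.D). The three-week phase-in changes the content and length of sessions, not their weekly number.
- Diary collection and questioning: every 4 weeks (Section III.D, Home exercise).
- Programme length: up to 12 weeks (Section I, Specific Aim 2).

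**Step 1: which routes could bring a home event to staff before the 4-weekly collection?**

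| Route | In the documents? | Timing specified? |
|---|---|---|
| Spontaneous report by the participant | Yes, in general terms, in the HIIT paragraph | No instruction on when to report a home event |
| Staff question at a supervised session | Events at supervised sessions are recorded; no question about home sessions is described | No |
| App diary | Yes, as an option | No review frequency |
| Paper diary | Yes, as an option | No review described before collection |
| Diary collection with questioning | Yes | Every 4 weeks |

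Only the last row has a schedule.

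**Step 2: how long could an event recorded only in the diary go unseen?**
- Longest delay: 4 weeks × 7 days = about 28 days, for an event early in an interval.
- If such events fell evenly over the interval, the average delay would be 28 / 2 = 14 days.

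**Step 3: how much further exercise is prescribed in that time?**
- Sessions in one interval: (3 + 3) × 4 = 24, of which 12 are supervised and 12 are at home.
- After an event in the first session of the interval, if that is a home session: 24 − 1 = 23 remain, made up of 12 supervised and 11 home sessions.
- Over 12 weeks there are 12 / 4 = 3 collections per participant.

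**Step 4: what would the existing contacts offer if they were used?**
- Three supervised sessions a week give an average spacing of 7 / 3 ≈ 2.3 days when all are attended, against 28 days between scheduled collections.

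**The case against.** The strongest reply is that the plan does not confine capture of home events to the 4-weekly collection. The 4-weekly question is expressly for events that have not come to light by other means, so it is a backstop. Participant report is named, participants meet staff three times a week, and the diary may be kept in an app. Immediate reporting also reads naturally as running from the time the team learns of an event, since nobody can forward what they do not know. On that reading the sections can coexist. All of this stands, and it rules out calling the text a strict contradiction. It does not close the gap: the other means are never defined for home events, and nothing ensures that staff learn of one in time.

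Three stronger readings are tempting and should be resisted.

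- **That PI evaluation before further sessions is already breached for home events.** That rule sits in the HIIT intervention paragraph, and the Home exercise paragraph does not repeat it. Its wording about future sessions could be read to cover home events, but the text does not say so.
- **That 4-weekly collection under-counts minor events in the <5% safety criterion (Hypothesis 2A).** An entry in a diary of home sessions that is read late is not a 4-week recall, and a late-read event still enters the numerator. The extra question can only add events. The documents do not show an under-count.
- **That half of all sessions are affected.** Home sessions are indeed half of those prescribed (3 × 12 = 36 of 72 per participant over a full 12 weeks). But only events written solely in the diary, and not otherwise mentioned, are exposed, and their number is unknown.

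**Conclusion.** The point holds as an unspecified pathway. The plan promises immediate reporting of any adverse event but gives home-session events no prompt route to staff, and its only scheduled capture for them is 4-weekly. The worst case is about 28 days unseen, with up to 23 further prescribed sessions. That bound assumes an event early in an interval, written only in the diary, not volunteered at any supervised session, and not noticed in the app. How often this would happen cannot be worked out from the documents.

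The consequence is a delay in the safety information available to the monitor and the PI. No bias in the Aim 2 safety result has been shown. This is a change worth making because it is cheap and the contacts it needs are already in the plan; it does not call the design into question.

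**What to change.** 1. Reconcile Section III.C (HIIT exercise intervention) with the HIIT intervention, Home exercise and Additional safety measures parts of Section III.D, so that they describe one pathway for home-session events. State when the immediate-reporting clock starts. State also whether the PI-evaluation step in the HIIT paragraph applies to events at home; that decision belongs to the investigators and the monitor.
2. At each existing supervised session, ask one recorded question about adverse events in home sessions since the last contact, and look at the diary, whether app or paper. Participants with paper diaries would need to bring them.
3. Keep the 4-weekly collection and questioning as a catch-all, which also covers participants who miss supervised sessions.

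The cost is about a minute of staff time per supervised session (an assumption). Over a full programme that is 3 × 12 = 36 sessions, or about 36 minutes per participant. Because staff time is itself an outcome under Hypothesis 2C, those minutes should be logged there. No new visits or staff are needed.
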